2.4.4.3 Multiplicity issues

All secondary endpoints will be exploratory and descriptive and therefore no adjustments for multiplicity are specified.

2.4.5 Analyses of safety endpoints

The summary of safety and tolerance results will be presented by treatment group.

All safety analyses will be performed on the safety population using the following common rules:

- The baseline value is defined as the last available value prior to the first injection of IMP,
- There are no safety endpoints which are adjudicated.

The baseline values for all safety analyses are defined as the last available value prior to the first dose of randomized treatment. Given the short half-life for duration of action of insulin, the TEAE reporting period is up to one day after last administration of IMP.

The analysis of the safety variables is essentially descriptive and no systematic testing is planned.

In addition, for hypoglycemia events, relative risks and odd-ratios with their associated 95% CI will be provided.

2.4.5.1 Analyses of hypoglycemia

All safety analyses of hypoglycemia events will be performed by actual treatment arm in the safety population, using events occurring during TEAE period.

- At time of 6-month database lock during:
 - The 6-month on-treatment period.
- At time of 12-month database lock during:
 - The 12-month on-treatment period but also,
 - The 6-month on-treatment period,
 - The 6 to 12 month on-treatment period.

The number and proportion of patients experiencing at least one hypoglycemia event and the number and rate (per patient-year of exposure) of hypoglycemic events will be presented by treatment arm and type of hypoglycemia event ([Appendix A](#)) according to time of occurrence:

- Nocturnal (defined by clock time: 00:00^{AM}-5:59^{AM}),
- Daytime (defined by clock time: 6:00^{AM}-23:59),
- And at any time of the day.

during each on-treatment period (as defined above).

Any hypoglycemia and un-classified ones (if any) will also be presented by treatment arm.

The incidence of hypoglycemia will be analyzed using logistic regression, adjusting for randomization strata: HbA1c target, SU use (y/n) and GLP-1 RA use (y/n), as well as baseline HbA1c (as continuous).

The rate per patient-year of hypoglycemic events will be analyzed using an over-dispersed Poisson regression model, adjusting for randomization strata. The model will include the logarithm of the duration of the considered on-treatment period (in years) as an offset variable and a log-link function.

Cumulative mean number of severe and/or symptomatic documented (≤ 70 mg/dL and < 54 mg/dL) hypoglycemia will be summarized over time using Nelson-Aalen estimates and plotted.

Subgroup analyses

The proportion of patients with at least one:

- Severe and/or symptomatic documented (≤ 3.9 mmol/L [≤ 70 mg/dL]) hypoglycemia,
- Severe and/or symptomatic documented (< 3.0 mmol/L [< 54 mg/dL]) hypoglycemia.

during respectively the 6-month on-treatment period and the 12-month on-treatment period (any time of the day), will also be presented by the following subgroups:

- Gender (male, female),
- Randomization strata of individualized HbA1c target ($< 8\%$ / $< 7\%$),
- Randomization strata of GLP-1 use (yes/no),
- Randomization strata of SU use (yes/no),
- Baseline HbA1c category ($< 9\%$ / $\geq 9\%$),
- Age group (< 65 , [65-75] and ≥ 75 years of age),
- Baseline BMI categories (< 25 , [25-30], [30-40] and ≥ 40 kg/m²),
- Category of duration of diabetes (< 10 , ≥ 10 years).

and analyzed using a similar logistic regression model approach as presented previously, but adding the corresponding subgroup factor and treatment arm-by-subgroup interaction factor. Odds ratio estimates and 95% CI will be provided in each subgroup category.

The interaction treatment arm-by-subgroup p-value will be provided for descriptive propose.

When the subgroup considered is equal to one of the randomization strata or is part of one of the adjustment factor, this randomization stratum/adjustment factor is removed from the model.

If the logistic regression model does not converge (eg, due to sparse data) some of the randomization strata may be removed.

Forest plots will be provided.

Relative Risks

For each hypoglycemic category of event ([Appendix A](#)) except relative and probable, the estimated proportions along with their corresponding 95% CI, as well as the relative risk of Toujeo arm versus SOC basal insulin arm and their corresponding 95% CI, will be estimated by the mean of a log-binomial regression model, using a log-link function and a binomial response distribution, and adjusting for:

- Randomization strata HbA1c target,
- Randomization strata of SU use (y/n),
- Randomization strata of GLP-1 RA (y/n),
- Baseline HbA1c (as continuous).

Risk difference

For each hypoglycemic category of event ([Appendix A](#)) except relative and probable, the adjusted risk differences of Toujeo arm versus SOC basal insulin arm and their corresponding 95% CI, will be estimated by the mean of a log binomial regression model, with an identity link function and a binomial response distribution, and adjusting for:

- Randomization strata HbA1c target,
- Randomization strata of SU use (y/n),
- Randomization strata of GLP-1 RA (y/n),
- Baseline HbA1c (as continuous).

Scatter plots

Scatter plots of Relative Risk versus Risk Difference presenting each type of analyzed hypoglycemia for patient experiencing at least one hypoglycemia event.

- During respectively the 6-Month on-treatment period and the 12-Month on-treatment period,
- According to time of occurrence (any time of the day, nocturnal [defined by clock time: 00:00^{AM}-5:59^{AM}]).

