2.1.4 Safety endpoints

The following safety parameters will be analyzed in the clinical study report:

- Hypoglycemia (according to American Diabetes Association [ADA] Workgroup on Hypoglycemia) (2),
- AEs, SAEs,
- Injection site reactions,
- Hypersensitivity reactions,
- Vital signs, and,
- Healthcare resource utilization including hospitalizations and emergency department or other provider visits and healthcare costs.

Observation period for safety endpoints

- The **pre-treatment period** is defined as the time from informed consent up to the time of the first injection of IMP.
- The **12-month on-treatment period** is defined as the time from the 1st IMP intake up to 1 day after the trial is completed².
- The **6-month on-treatment period** named “Month 1 to Month 6” is defined as the time from 1st IMP intake up to Day 180 (Visit 3) or 1 day after date of last insulin (either IMP or commercial basal insulin prescribed following a switch) or 6-month visit, whichever comes earlier³.
- The **6 to 12-month on-treatment period** named “from start of Month 7 to Month 12” is defined as the time from the day following the 6-month on-treatment period up to the end of the 12-month on-treatment period².
- The **post-treatment period** is defined as the time starting 2 days after last injection of IMP (after the on-treatment period).
- The **on-study observation period** is defined as the time from randomization until the end of the study (defined as last protocol planned visit or the resolution/stabilization of all SAEs and AE with pre-specified monitoring).

2. Used at time of 12 month database lock,

3. Used for 6 month and 12 month database lock.

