2.3 ANALYSIS POPULATIONS

Patients treated without being randomized will not be considered randomized and will not be included in any safety or efficacy population.

Patients who are dispensed/prescribed study drug without calling the IRT or before calling the IRT are considered non-randomized patients. They are excluded from any population for analysis, including efficacy and safety. However, if these patients experienced any significant safety event, they should be documented separately in the clinical study report.

The randomized population includes any patient who has signed her/his informed consent and has been allocated to a randomized treatment arm regardless of whether the treatment was delivered or used.

The safety and efficacy populations will be defined at time of 6-month data base-lock based on data collected during the 6 month-randomized period.

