2.3.2 Safety population

The safety population is defined as: all randomized patients who actually received at least one dose or part of a dose of IMP, analyzed according to the treatment actually received.

In addition:

- Non-randomized but treated patients will not be part of the safety population. This is a post marketing real world trial with commercially available insulin so that non-randomized but treated patients are not considered part of the trial and safety data are listed separately.
- Randomized patients for whom it is unclear whether they took the study medication will be included in the safety population as randomized.
- For any patient receiving more than one study treatment (Toujeo or “standard of care” basal insulin) during the trial, the patient will be analyzed in the treatment arm in which he/she was treated longer by either IMP (allocated by IRT or prescribed/dispensed) or Commercial basal insulin prescribed following a switch during the 6-month on-treatment period. This actual treatment arm, defined at time of 6-month database lock on the 6-month on-treatment period, will be applied at time of 12-month database lock (ie, to the 12-month on-treatment period).

If a patient is randomized more than once, only the data associated with the first randomization are used in the analysis population. The subject will be analyzed according to the first randomization treatment arm. All data collected after the second randomization will be excluded from the primary efficacy analysis. The safety experience associated with any later randomization is described separately.

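### Hypoglycemia incidence for the 6 to 12 month period has no at-risk denominator, so patients who left before it count as event-free and incidence is understated in proportion to their share

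*SAP*

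**What the plan says.** - **Analysis set.** SAP 2.4.5.1: "All safety analyses of hypoglycemia events will be performed by actual treatment arm in the safety population, using events occurring during TEAE period". At the 12-month lock this covers the 12-month, the 6-month and the 6 to 12 month on-treatment periods. For each period the SAP presents the proportion of patients with an event and the event rate.
- **Membership.** SAP 2.3.2 defines the safety population as "all randomized patients who actually received at least one dose or part of a dose of IMP". Nothing requires presence after Month 6. SAP 2.3 adds: "The safety and efficacy populations will be defined at time of 6-month data base-lock based on data collected during the 6 month-randomized period".
- **Incidence model.** SAP 2.4.5.1: "The incidence of hypoglycemia will be analyzed using logistic regression, adjusting for randomization strata", together with baseline HbA1c. It has no exposure term. The over-dispersed Poisson model for the rate, in the same section, has the log of the period's duration as an offset.
- **Window.** SAP 2.1.4 says that the 6 to 12 month period "is defined as the time from the day following the 6-month on-treatment period up to the end of the 12-month on-treatment period", and that the 12-month period "is defined as the time from the 1st IMP intake up to 1 day after the trial is completed". SAP 2.4.5 has a different end point: "the TEAE reporting period is up to one day after last administration of IMP".
- **At-risk subset.** None is defined for the later window. The 6-month completers appear only under disposition (SAP 2.2).

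**The concern.** An event in the 6 to 12 month period can be recorded only in a patient who is observed during it. A patient who took one dose and left the study in Month 3 is in the safety population, has no observation in the later window, and cannot be anything but event-free there. Absence of data is then read as absence of hypoglycemia.

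Three consequences follow. Incidence in that window is too low in any arm that lost patients. If loss of follow-up differs between arms, the arm that loses more looks safer. And incidence and rate for the same window rest on different patients: a zero duration has no logarithm, so a patient with no time in the window cannot enter the Poisson model but stays in the incidence denominator.

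**Working it through.** **Plan's own figure.** The documents state no incidence for this window, no event count and no dropout rate, so there is nothing to reproduce. The values of p and d below are assumptions, shown over a range.

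**Step 1: does the text make leavers non-events?**
- SAP 2.4.5.1 names the analysis set but not a denominator. The adverse event section (SAP 2.4.5.2) does name one: the safety population within each arm.
- SAP 2.5.3 leaves missing categorical data out of percentages unless otherwise specified. That would remove leavers only if their status were set to missing, and no rule in the safety section does so.
- Elsewhere the SAP does deal with the case. In the multiple-imputation sensitivity analysis (SAP 2.4.4.1), a dropout with no recorded event has missing hypoglycemia status. For the composite endpoints (SAP 2.5.2), premature end of study is a failure.

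The plain reading is therefore the full safety population, with leavers event-free.

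**Step 2: one arm.** Let N be the arm's safety population, d the share with no observed time in the window, and p the incidence among the rest.
- Planned incidence = p × N(1 − d) / N = p(1 − d).
- With an at-risk denominator = p × N(1 − d) / [N(1 − d)] = p.
- Relative shortfall = d; shortfall in percentage points = p × d.

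| d (assumed) | Shown when p = 20% | Shortfall, points |
|---|---|---|
| 10% | 0.20 × 0.90 = 18% | 2 |
| 15% | 0.20 × 0.85 = 17% | 3 |
| 20% | 0.20 × 0.80 = 16% | 4 |
| 25% | 0.20 × 0.75 = 15% | 5 |
| 30% | 0.20 × 0.70 = 14% | 6 |

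Over d from 5% to 30% and p from 10% to 40%, the shortfall runs from 0.05 × 0.10 = 0.5 points to 0.30 × 0.40 = 12 points.

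**Step 3: between arms.** Planned relative risk = true relative risk × (1 − d_Toujeo) / (1 − d_comparator).
- Equal d: the factor is 1 and the relative risk is unchanged. A true risk difference shrinks by the factor (1 − d).
- d of 15% (Toujeo) against 25% (comparator), p = 20% in both: 17.0% against 15.0%. Relative risk 0.85/0.75 = 1.13; odds ratio (0.17/0.83)/(0.15/0.85) = 1.16, where equal p gives 1.00.
- d of 10% (Toujeo) against 20% (comparator): relative risk 0.90/0.80 = 1.125. With the shares reversed: 0.80/0.90 = 0.889.

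**Step 4: who belongs in d?** This is exact for patients who left the study. For those who stopped insulin but stayed, SAP 2.1.4 and 2.4.5 give different answers. Under 2.1.4, their 6-month period ends one day after the last insulin, so the later window opens the next day and runs to trial completion. Under the TEAE cut-off, counting stops one day after the last IMP dose. If their events count, the shortfall is smaller. For example, if the share d had half the incidence of the others, the table would show p(1 − d) + 0.5pd = p(1 − d/2), a relative shortfall of d/2.

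**The case against.** **The denominator is inferred.** This stands as a limit. SAP 2.4.5.1 does not use the word. The reading rests on the named analysis set, agrees with the adverse event section, and is not contradicted by any missing-status rule for leavers. If an at-risk denominator is already intended, it needs to be written down.

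**The 6-month lock as cause.** A reader might infer that fixing the population at the 6-month lock creates the problem. It does not. The same early leavers would be in a population defined at 12 months, because one dose suffices. The cause is the membership rule without an at-risk restriction.

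**Persistence as evidence of unequal loss.** A reader might also infer that unequal loss is expected because persistence and withdrawal are compared by arm. Those endpoints (SAP 2.4.3.2, 2.5.2) concern staying on treatment. Protocol 10.3.3 asks patients who stop to go on reporting hypoglycemia and to return at Day 180, and encourages them to stay to Day 360. Protocol 10.3.4 sets Day 180 as the minimum follow-up, so gaps after Month 6 are plausible. Nothing in the documents indicates that they differ by arm.

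**The stakes are low.** This is largely right. The hypoglycemia variables in SAP 2.1.4.1 run from baseline to 6 and to 12 months, and the later window is an extra breakdown. SAP 2.4.5 calls the safety analysis essentially descriptive. The rate with its offset and the Nelson-Aalen estimates already account for follow-up time.

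**The remedy is partial.** Also right. A patient who leaves in Month 8 is still only partly observed, and those who remain are a post-randomization subset.

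**Conclusion.** The concern holds, for one descriptive safety breakdown. As written, incidence for the 6 to 12 month period becomes p(1 − d): too low in relative terms by the share of patients with no observed time in the window. The shortfall in percentage points is p × d, not d.

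The size in this trial is unknown, because the documents give neither dropout nor incidence for the window; 18% to 14% in place of 20% rests on an assumed d of 10% to 30%. The relative risk is distorted only under unequal loss, and the odds ratio of 1.16 rests on a chosen 15% against 25% split. Neither is evidence that a bias between arms will occur.

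The mismatch between rate and incidence does not depend on those assumptions: it arises as soon as any safety-population patient has no time in the window. The primary endpoint and the 0 to 6 month incidence are untouched.

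**What to change.** In SAP 2.4.5.1, for the 6 to 12 month on-treatment period only:

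1. Base the proportion, the logistic model and, where they are run for this period, the relative-risk and risk-difference models on safety-population patients with at least one day of observed time in the period. Use the same patients in the rate model.
2. Show that number per arm beside the safety-population total.
3. Reconcile the window in SAP 2.1.4 with the TEAE cut-off in SAP 2.4.5 and 2.4.5.1, and define the flag on the reconciled window. A flag set at calendar Month 7 would not match a window that can open earlier for patients who stop insulin early.
4. Label the comparison descriptive and as being among patients still observed.

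Keep the full safety population for the 0 to 6 and 0 to 12 month analyses.

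The cost is a few sentences of SAP text and one population flag; no new data are needed. The downside is that the later-window comparison is openly made in a post-randomization subset and loses the protection of randomization. Patients who leave during the window remain partly observed; the rate and Nelson-Aalen analyses address that.

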2.4.5.2 Analyses of adverse events

Generalities

All safety analyses of hypoglycemia events will be performed by actual treatment arm in the safety population. The primary focus of AE reporting will be on TEAEs. Pre-treatment and post-treatment AEs will be described separately.

The primary focus of AE reporting will be:

- At time of 6 month database lock: 6 month on-treatment AE, occurring during the 6 month on-treatment period.
- At time of 12 month database lock: on treatment-emergent adverse events, occurring during the 12 month on-treatment period.

Pre-treatment and post-treatment AEs will be described separately.

Post-treatment AE will only be displayed at time of 12-month database lock but also at time of 6 month database lock for patients who permanently discontinued treatment during the 6 month randomized period.

If an AE date/time of onset (occurrence, worsening, or becoming serious) is incomplete, an imputation algorithm will be used to classify the AE as pre-treatment, treatment-emergent, or post-treatment. The algorithm for imputing date/time of onset will be conservative and will classify an AE as treatment-emergent unless there is definitive information to determine it is pre-treatment or post-treatment. Details on classification of AEs with missing or partial onset dates are provided in [Section 2.5.3](#).

Adverse event incidence tables will present by SOC, HLG, HLT, and PT, sorted in alphabetical order for each treatment group, the number (n) and percentage (%) of patients experiencing an AE. Multiple occurrences of the same event in the same patient will be counted only once in the tables within a treatment phase. The denominator for computation of percentages is the safety population within each treatment group.

Sorting within tables ensures the same presentation for the set of all AEs within the observation period (pre-treatment, treatment-emergent, and post-treatment). For that purpose, the table of all treatment-emergent adverse events presented by SOC and PT sorted by the internationally agreed SOC order and decreasing frequency of PTs within SOCs will define the presentation order for all other tables unless otherwise specified. Sorting will be based on results for the IMP.

Analysis of all treatment-emergent adverse events

The following treatment-emergent adverse event summaries will be generated for the safety population.

- Overview of treatment-emergent adverse events, summarizing number (%) of patients with any,
 - Treatment-emergent adverse event,
 - Serious treatment-emergent adverse event,
 - Treatment-emergent adverse event leading to death,
 - Treatment-emergent adverse event leading to permanent treatment discontinuation,
 - Treatment-emergent adverse event related to IMP,
 - Treatment-emergent adverse event related to anti-diabetic NIMP,
 - Treatment-emergent adverse event related to pen device.

- All treatment-emergent adverse event by primary SOC, HLG, HLT, and PT, showing number (%) of patients with at least 1 treatment-emergent adverse event sorted by the SOC internationally agreed order. The other levels (HLG, HLT, PT) will be presented in alphabetical order.
- Number (%) of patients experiencing TEAE(s) presented by PT, sorted by decreasing incidence of PT in the Toujeo arm.
- All treatment-emergent adverse events by primary SOC and PT, showing the number (%) of patients with at least 1 treatment-emergent adverse event, sorted by the internationally agreed SOC order and by decreasing incidence of PTs in the Toujeo arm within each SOC. This sorting order will be applied to all other tables, unless otherwise specified.
- All common TEAEs (HLT incidence $\geq 2\%$ in any treatment arm) by primary SOC, HLT and PT, showing the number (%) of patients with at least 1 common TEAE, sorted by the internationally agreed SOC order. The other levels (HLT, PT) will be presented in alphabetical order.
- All treatment-emergent adverse events regardless of relationship and related to IMP by primary SOC, HLG, HLT and PT, showing the number (%) of patients with at least 1 treatment-emergent adverse event, sorted by the internationally agreed SOC order. The other levels (HLG, HLT, PT) will be presented in alphabetical order.
- All treatment-emergent adverse events regardless of relationship and related to anti-diabetic NIMP by primary SOC, HLG, HLT and PT, showing the number (%) of patients with at least 1 treatment-emergent adverse event, sorted by the internationally agreed SOC order. The other levels (HLG, HLT, PT) will be presented in alphabetical order.
- All treatment-emergent adverse events regardless of relationship and related to pen device by primary SOC, HLG, HLT and PT, showing the number (%) of patients with at least 1 treatment-emergent adverse event, sorted by the internationally agreed SOC order. The other levels (HLG, HLT, PT) will be presented in alphabetical order.
- All treatment-emergent adverse events by maximal severity, presented by primary SOC and PT, showing the number (%) of patients with at least 1 treatment-emergent adverse event by severity (ie, mild, moderate, or severe), sorted by the sorting order defined above,
- Number (%) of patients experiencing treatment-emergent adverse event(s) presented by primary and secondary SOC, HLG, HLT, and PT sorted by the internationally agreed SOC order. The other levels (HLG, HLT, PT) will be presented in alphabetical order.

Analysis of all treatment-emergent serious adverse event(s)

- All treatment-emergent SAEs by primary SOC, HLG, HLT, and PT, showing the number (%) of patients with at least 1 serious treatment-emergent adverse event, sorted by the internationally agreed SOC order. The other levels (HLG, HLT, PT) will be presented in alphabetical order.
- All treatment-emergent SAEs regardless of relationship and related to IMP, by primary SOC, HLG, HLT, and PT, showing the number (%) of patients with at least 1 treatment-emergent SAE, sorted by the internationally agreed SOC order. The other levels (HLG, HLT, PT) will be presented in alphabetical order.

Analysis of all treatment-emergent adverse event(s) leading to treatment discontinuation

- All treatment-emergent adverse events leading to treatment discontinuation, by primary SOC, HLG, HLT, and PT, showing the number (%) of patients sorted by the internationally agreed SOC order. The other levels (HLG, HLT, PT) will be presented in alphabetical order.

Injection site reaction and hypersensitivity reaction

- Number (%) of patients with events related to injection site reactions and hypersensitivity reactions will be provided separately.

Adverse event of special interest

Symptomatic overdose

- A listing of patients with symptomatic overdose with IMP/NIMP will be provided.

ALT increase

- A listing of patients with increase of ALT (collected as an AE) will be provided.

Pregnancy

- A listing of patients with pregnancy (including event occurring to a partner) will be provided.

Analysis of pre-treatment and post-treatment adverse events

- All pre-treatment AEs by primary SOC and PT, showing the number (%) of patients with at least 1 pre-treatment AE, sorted by the internationally agreed SOC order and decreasing incidence of PTs within each SOC.
- All pre-treatment SAEs by primary SOC and PT, showing the number (%) of patients with at least 1 post-treatment SAE, sorted by the internationally agreed SOC order and decreasing incidence of PTs within each SOC.
- All pre-treatment AEs leading to study discontinuation by primary SOC and PT, showing the number (%) of patients, sorted by the internationally agreed SOC order and decreasing incidence of PTs within each SOC.
- All post-treatment AEs by primary SOC and PT, showing the number (%) of patients with at least 1 post-treatment AE, sorted by the internationally agreed SOC order and decreasing incidence of PTs within each SOC.
- All post-treatment SAEs by primary SOC and PT, showing the number (%) of patients with at least 1 post-treatment serious AE, sorted by the internationally agreed SOC order and decreasing incidence of PTs within each SOC.

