2.4.5.3 Deaths

The following deaths summaries will be generated on the safety population:

- Number (%) of patients who died by study period (pre-treatment, on-study, on-treatment, post-study) and reasons for death summarized by treatment arm,
- Death in non-randomized patients or randomized and not treated patients,
- TEAE leading to death (death as an outcome on the AE CRF page as reported by the Investigator) by primary SOC, HLG, HLT and PT showing number (%) of patients sorted by internationally agreed order of SOC and alphabetic order of HLG, HLT, and PT presented in alphabetic order within SOC.
- All pre-treatment AEs leading to death by primary SOC and PT, showing the number (%) of patients, sorted by the internationally agreed SOC order and decreasing incidence of PTs within each SOC (if more than 5 patient with the event),
- All post -treatment AEs leading to death by primary SOC and PT, showing the number (%) of patients, sorted by the internationally agreed SOC order and decreasing incidence of PTs within each SOC (if more than 5 patient with the event).

A listing of all deaths sorted by treatment arm will be performed.

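### The table of pre-treatment AEs leading to study discontinuation is built on dosed patients, so it omits those who left because of an AE before any dose

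*SAP*

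**What the plan says.** SAP 2.4.5 sets one population for the whole safety section: "All safety analyses will be performed on the safety population using the following common rules". SAP 2.4.5.2 repeats it for the AE tables: "The denominator for computation of percentages is the safety population within each treatment group". It says that pre-treatment and post-treatment AEs are described separately, but names no other population for them. Protocol 11.4.3 has the same rule.

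SAP 2.3.2 defines the safety population as "all randomized patients who actually received at least one dose or part of a dose of IMP", analysed by treatment actually received, with one extension: "Randomized patients for whom it is unclear whether they took the study medication will be included in the safety population as randomized". Protocol 11.3.2 agrees on both.

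SAP 2.1.4 fixes the period: the pre-treatment period "is defined as the time from informed consent up to the time of the first injection of IMP".

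Within these rules SAP 2.4.5.2 plans tables of pre-treatment AEs, of pre-treatment SAEs, and of those AEs that led to leaving the study: "All pre-treatment AEs leading to study discontinuation by primary SOC and PT, showing the number (%) of patients". The SAE line reads "All pre-treatment SAEs by primary SOC and PT, showing the number (%) of patients with at least 1 post-treatment SAE".

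SAP 2.4.5.3 generates its death summaries on the safety population, and one of them is "Death in non-randomized patients or randomized and not treated patients". The same section ends with a listing of all deaths by treatment arm.

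**The concern.** The period and the population meet at the same moment, the first injection, from opposite sides. A pre-treatment AE must start, worsen or become serious before that injection, whereas membership of the safety population normally begins with it. For a table about leaving the study because of such an AE, the typical patient never reaches the injection and so never enters the population.

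This case is foreseeable. In the US a patient leaves the randomization visit with a prescription and a reimbursement card and obtains the insulin at a pharmacy (Protocol 8.4 and 10.1.1.2), so allocation and first dose can be separated in time. SAP 2.2 has its own disposition category for randomized patients who were not treated. The trial is open label, so it is useful to see by randomized arm what happened between known allocation and first dose. A near-empty discontinuation table could be misread as showing that almost nobody left because of an early AE.

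**Working it through.** No figure in the plan is at stake, and no arithmetic applies. The check is to apply the SAP's definitions to each kind of patient with a pre-treatment AE.

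**Inputs.** Population rule: SAP 2.4.5 and 2.4.5.2. Population definition and its extension: SAP 2.3.2. Period: SAP 2.1.4. Tables: SAP 2.4.5.2. Deaths: SAP 2.4.5.3.

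**Step 1: the discontinuation table.** Let S be the safety population and D the patients who left the study because of a pre-treatment AE. The table shows D ∩ S.

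| Patient in D | In S? | Shown? |
|---|---|---|
| Consented, left before randomization | No, not randomized | No |
| Randomized, known not to be dosed | No, no dose | No |
| Randomized, dosing unclear | Yes, by the extension | Yes |
| Randomized, dosed anyway, left later because of that AE | Yes | Yes |

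The first two rows are the patients for whom the table is planned, and both are lost. The last two keep the table from being empty by definition.

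**Step 2: the general pre-treatment AE and SAE tables.** These are not conditional on leaving. Any patient who has an event between consent and first injection and is then dosed belongs to S and is shown. Among randomized patients, only events in those known to be undosed are lost.

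**Step 3: deaths.** A patient who was never randomized cannot be in S. A randomized patient known to be untreated is not in S either. Under its own header the summary of deaths in these two groups therefore has no members. The closing listing of all deaths carries no limit to dosed patients in its own sentence.

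**Step 4: the SAE line.** Its subject is pre-treatment SAEs and its count is patients with a post-treatment SAE. It stands between two pre-treatment lines, and a separate post-treatment SAE line follows. The line contradicts itself.

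**Step 5: other outputs for undosed patients.** SAP 2.2 reports screen failures with reasons and counts randomized but untreated patients, and SAP 2.2.1 lists the latter. None of these is a table of AEs.

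**The case against.** The strongest reply is that little is lost. AEs are recorded from consent and are to be included in the study report (SAP 2.1.4.2), and SAEs are entered within 24 hours (Protocol 10.4.4). The untreated-death line names its own group, so a sensible reader takes it as an exception to the header. Some randomized non-starters may also enter the safety population through the unclear-dosing rule, because US sites keep no treatment log (Protocol 8.8). The safety analysis is essentially descriptive, and the primary analysis uses all randomized patients (SAP 2.3.1 and 2.4.4.1).

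All of this stands, and it limits the point. It does not repair the discontinuation table, for which no other population is given, and the death line still has to be read against its header to be produced at all.

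A reader might go further and infer three things that the documents do not support:

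- **That all the pre-treatment tables show about zero events.** The general AE and SAE tables keep every event of patients who were later dosed.
- **That serious events before the first dose go unreported.** They are collected and individually reported; what is missing is their place in the by-arm tables.
- **That the plan intends to count post-treatment SAEs in the pre-treatment table.** The position and subject of the line point to a copying slip.

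**Conclusion.** The point holds as a minor one. As specified, the table of pre-treatment AEs leading to study discontinuation leaves out the patients who left because of an AE before any dose. The general pre-treatment AE and SAE tables are incomplete only for undosed randomized patients, and the untreated-death summary conflicts with its header.

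The loss cannot be sized. The documents give neither a rate of randomized patients who never start insulin nor a rate of events before the first dose. Each assumed 1% of non-starters would be 0.01 × 3324 ≈ 33 patients, but these are patients, not events, and no document supports any particular percentage.

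The conclusion rests on reading the population rule in SAP 2.4.5 and 2.4.5.2 as applying to the pre-treatment tables, which is what the text says in the absence of an exception. The primary analysis, the significance levels and the sample size are not touched.

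**What to change.** - In SAP 2.4.5.2, name all randomized patients, by randomized arm, as population and denominator for the three pre-treatment tables: AEs, SAEs, and AEs leading to study discontinuation. Randomized arm is needed because an undosed patient has no treatment actually received.
- In SAP 2.4.5.3, use the same population for deaths in randomized but untreated patients, and take that line out from under the safety-population header.
- List the pre-treatment events and deaths of consented but non-randomized patients separately.
- As an editorial correction, replace post-treatment by pre-treatment in the count of the pre-treatment SAE line.

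The cost is a few lines of SAP text and a different population flag for a handful of tables. No new data are needed, since AEs are already recorded from consent.
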